1.1. Primary

- 1.1.1. To provide access to treatment with investigational convalescent plasma to inpatients with documented COVID-19 infection
- 1.1.2. To measure NAb titers in an aliquot of the CP administered, to measure the volume of CP administered, and determine whether there is a correlation between the NAb dose (in NAb units/kg body weight, where a unit is the reciprocal of the endpoint NAb titer in the CP multiplied by the volume in ml) and change or lack of change when comparing pre-treatment and day one NAb titers.

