There are reports that convalescent serum was used for therapy of patients with COVID-19 in China during the current outbreak. In an open label study, 5 patients received transfusion with convalescent plasma with a SARS-CoV-2– specific antibody (IgG) binding titer greater than 1:1000 (end point dilution titer, by enzyme-linked immunosorbent assay [ELISA]) and a neutralization titer greater than 40 (end point dilution titer) that had been obtained from 5 patients who recovered from COVID-19 (Shen 2020). Convalescent plasma was administered between 10 and 22 days after admission. In this preliminary uncontrolled case series of 5 critically ill patients with COVID-19 and ARDS, administration of convalescent plasma containing neutralizing antibody was followed by improvement in their clinical status.

In another study, 10 patients were treated with one dose of 200 mL convalescent plasma (CP) derived from recently recovered donors with the neutralizing antibody titers above 1:640 in addition to maximal supportive care and antiviral agents Duan 2020). The clinical symptoms were significantly improved along with increase of oxyhemoglobin saturation within 3 days. Several parameters tended to improve as compared to pre-transfusion, including increased lymphocyte counts ($0.65 \times 10^9/L$ vs. $0.76 \times 10^9/L$) and decreased C-reactive protein (55.98 mg/L vs. 18.13 mg/L). Radiological examinations showed varying degrees of absorption of lung lesions within 7 days. In none of these two trials serious adverse events associated with the use of CP were reported.

More recently, the FDA has endorsed the use of CP under an emergency IND, specific guidance on donor and potential recipient selection has been published. (<https://www.fda.gov/media/98616/download>)

Little is known about how the treatment with CP affects the recipient's immune response to the infection with SARS-CoV-2. What levels of neutralizing antibodies (NAb) are obtained in patients transfused? Is there association between neutralizing antibody titers and clinical outcomes? In the study by Duan et al, with 10 patients treated with CP, the neutralizing antibody titers of five patients increased and four patients remained at the same level after CP transfusion. However, neither study performed a comparison between the NAb dosing adjusted for body weight versus resulting NAb levels in recipients.

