PROTOCOL TITLE: Open, non-comparative pilot study to provide access to treatment with investigational convalescent plasma and measure antibody levels in patients hospitalized with COVID-19

transfusion related infection, hemolytic transfusion reaction or evidence of antibody dependent enhancement of infection (ADE).

8. Research Setting

The study will be conducted in the University of New Mexico Hospital. Patients admitted to the COVID-19 units including the emergency department, regular wards and intensive care units will be enrolled. Patients will be identified from the TriCore Laboratory testing result portal available to the research team or upon notification by providers in the participating institutions. Approval by the treating provider will be requested before patient enrollment and consent.

There is no external sponsor for this research. Immune assays and genomic studies will be performed utilizing existing resources within the [name] and [name] laboratories in the Center for Global Health.

SARS-CoV-2 neutralizing antibody titers will be measured using the focus reduction neutralization test (FRNT) in [name] Laboratory, Center for Global Health (CGH), UNMHSC. Neutralization assays will be conducted using methods already established in the [name] laboratory. Briefly, serial dilutions of plasma will be incubated with 50-100 pfu of SARS-CoV-2 at equal volumes for 1 hour and added to Vero E6 cells, followed by overlaying with agarose. Two days later cells will be fixed with 4% formaldehyde, stained with crystal violet, and plaques will be counted. Other functions of antibody, including antibody-dependent cell-mediated cytotoxicity and complement-dependent cytotoxicity, will be ascertained using established methods.

Virus sequencing will be performed in the laboratory of [name] in the Center for Global Health using the PCR-based NGS sequencing protocol described by the ARTIC Network <https://artic.network/ncov-2019>

9. Resources Available

9.1. Principal investigator and co-investigators are experienced Pulmonary, Critical Care, Infectious Disease ID Pharmacists, Virologist or Transfusion Medicine specialists with ample experience in conducting clinical trial and with the use of CP in previous clinical studies (GM):

- 9.1.1. [name], is a Pulmonary and Critical Care Medicine specialist and is the Chief of the Division of Pulmonary at UNMH
- 9.1.2. [name], is an Infectious Disease Attending and is the Chief of Infectious Diseases at UNMH.

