PROTOCOL TITLE: Open, non-comparative pilot study to provide access to treatment with investigational convalescent plasma and measure antibody levels in patients hospitalized with COVID-19

- 12.1. Potential subjects will be identified by reviewing the registry of +SARSCoV2 RTPCR testing (at TRICORE laboratory) in hospitalized patients.
- 12.2. Eligibility of the potential study participants will be identified by their treating providers (Hospital Medicine and Intensive Care Unit). The treating providers will notify representatives of the research team. Members of the research team will verify the eligibility of the potential subjects and will obtain informed consent from them or their LAR.
- 12.3. Once the participant or their LAR gives their written informed consent, the research team will notify the treating provider so they can place the medical order for the investigational products. If LAR consented via phone, a copy of the consent form will be mailed to LAR.
- 12.4. The protocol specific activities are detailed in Table 1
- 12.5. Treatment

Subjects will receive the convalescent plasma.

Study drug: The investigational product is anti-SARS-CoV-2 convalescent plasma obtained from former patients identified as having recovered from COVID-19 and obtained by Vitalant from local and national donors following national blood donation guidelines. These donors will be cleared for blood donation like any other volunteer blood donor and samples will have been screened for transfusion-transmitted infections (e.g. HIV, HBV, HCV, WNV, HTLV-I/II, T. cruzi, ZIKV) both through the use of the uniform donor questionnaire and FDA mandated blood donor screening tests. This single-donor plasma product will have been collected using apheresis technology and in accordance with standard FDA and blood bank protocols.

A 1ml of aliquot of anti-SARS-CoV-2 plasma will be saved for NAb titer measurement by FRNT (as mention in section 8.) in the CGH laboratory and the total volume of plasma administration will be recorded.

 - 12.5.1. Study subjects will receive 1 unit (200mL) of SARS-CoV-2 convalescent plasma collected from a single donor who recovered from COVID-19.

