 - 12.5.2. The anti-SARS-CoV-2 convalescent plasma will be in standard plasma blood unit bags, anticoagulated with a citrate-based anticoagulant (ACD-A, CP2D, et cetera), labeled with a specific ISBT product code, and stored in the UNM Blood Bank per FDA, AABB, and CAP protocols. Plasma transfusion will be administered over no more than four hours.

Table 1: Schedule of Events

PROTOCOL TITLE: Open, non-comparative pilot study to provide access to treatment with investigational convalescent plasma and measure antibody levels in patients hospitalized with COVID-19

Study period	Screen	Baseline	Transfusion	Follow-up			
Day	-1 to 0	0	0	1	3	7	14
Eligibility							
Informed consent	x						
Demographic and Medical history	x						
SARS-CoV-2 RT-PCR for eligibility	x						
Pregnancy test	x						
Type and screen	x						
Study Agent Administration							
Plasma Transfusion			x				
Study Procedures							
Vital signs	x	x	xxxx[1]	x	x	x	x
Physical assessment	x		x	x		x	
Symptom screen	x	x	x	x	x	x	x
Concomitant medications	x	x	x				

PROTOCOL TITLE: Open, non-comparative pilot study to provide access to treatment with investigational convalescent plasma and measure antibody levels in patients hospitalized with COVID-19

Adverse event monitoring		x	x	x	x	x	x	
Laboratory testing								
SARS-CoV-2 RT-PCR^[2] and Genomic analysis		x			x	x	x	
SARS-CoV-2 neutralizing antibody		x		x	x	x	x	
Secondary End point registration (clinical outcome)								

1. Vital sign testing: Immediately prior to infusion, 10-20 minutes after start of infusion, at completion of infusion and 30-60 minutes after the end of the infusion
2. Sampling can include nasopharyngeal, nasal or oropharyngeal swabs.

13. Data Analysis

13.1.1. We will determine whether there is a correlation between the NAb dose (in NAb units/kg body weight, where a unit is the reciprocal of the endpoint NAB titer in the CP multiplied by the volume in ml) and change or lack of change when comparing pre-treatment and day one NAb titers. We will also compare changes in pre- and post-treatment NAb titers based on NAb dosing calculated in units/BSA and units/calculated plasma volume to see if either measurement provides a better prediction of changes in NAb titers in recipients.

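### The primary NAb dose uses an endpoint titre and the recipient read-out is unstated; if recipient titres are also read in dilution steps, small day-1 rises are only partly recorded and the dose-change correlation is weakened

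*Combined protocol and SAP*

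**What the plan says.** Sections 1.1.2 and 13.1.1 set up the same analysis. The exposure is NAb dose per kg, built from a unit "where a unit is the reciprocal of the endpoint NAb titer in the CP multiplied by the volume in ml". The response is "change or lack of change when comparing pre-treatment and day one NAb titers". No size of change is defined, and neither section says whether titres are analysed raw or on a log scale.

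Section 12.5.1 fixes the volume: "Study subjects will receive 1 unit (200mL) of SARS-CoV-2 convalescent plasma collected from a single donor". Section 2 says that plasma titres will initially not be known before transfusion, so low-titre units can occur.

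Section 7.1.1 names FRNT for recipient titres on days 0, 1, 3, 7 and 14, and section 12.5 names it for the plasma aliquot. Section 8 describes the assay: "serial dilutions of plasma will be incubated with 50-100 pfu of SARS-CoV-2 at equal volumes for 1 hour", after which the cells are "stained with crystal violet, and plaques will be counted". It gives no starting dilution, dilution factor, neutralization cut-off, interpolation rule or handling of values below the lowest dilution.

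The word *endpoint* is attached only to the plasma titre. Section 2 uses the same term, as an end-point dilution, for a cited five-patient series. On the cited 10-patient study, which gave 200 mL from donors with titres above 1:640, section 2 reports "neutralizing antibody titers of five patients increased and four patients remained at the same level after CP transfusion".

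**The concern.** An endpoint titre in the ordinary sense is the last dilution that still neutralizes, so it moves only in whole dilution steps. One unit of plasma is diluted in the recipient's own plasma, and the patients are already ill enough to be in hospital, so some will have antibody of their own. The true day-1 rise may then often be less than one step. If both samples are read in steps, many modest rises become ties and others are rounded up to a full step. Rounding the plasma titre adds some error to the exposure as well.

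At stake is the dose-response question in the primary objective. Section 13.2 says the results are to inform dosage in future work, and that recruitment or CP dosing may be revisited by amendment after an interim look at 10 patients. A correlation weakened by rounding could be taken as evidence that dose matters little.

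**Working it through.** **The plan's own figure.** The only sample-size figure is 30 subjects for a 20% margin of error (section 5). At 95% confidence this needs a coefficient of variation of 0.2 × √30 / 1.96 = 0.56, which is not stated, so the figure cannot be reproduced. It is used below only as n = 30.

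**Inputs.** From the documents: volume 200 mL; dose = reciprocal titre × mL / kg; n = 30; cited donor titre above 640. Assumed, because the documents give no value: plasma volume Vp 3.0 L (range 2.0-4.5 L), the dilution series, the titre distributions and the assay noise.

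**Size of the rise.** With donor titre D and day-0 titre T0, simple mixing gives

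- f = 200 / (Vp + 200)
- rise = f × (D − T0)
- fold change = (1 − f) + f × D/T0

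A twofold rise needs D/T0 ≥ (1 + f)/f = 1/f + 1.

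| Vp (L) | f | D/T0 needed for twofold | Largest T0 giving twofold at D = 640 |
|---|---|---|---|
| 2.0 | 200/2200 = 1/11 | 12 | 53 |
| 3.0 | 200/3200 = 1/16 | 17 | 38 |
| 4.5 | 200/4700 = 1/23.5 | 24.5 | 26 |

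**Chance that a rise is recorded.** If the baseline falls at random within a twofold step and there is no assay error, a rise of less than twofold crosses a step with probability log2(fold). At D = 640 and f = 1/16:

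| T0 | Fold change | Chance recorded |
|---|---|---|
| 20 | 15/16 + 40/20 = 2.94 | certain |
| 40 | 15/16 + 40/40 = 1.94 | 0.95 |
| 80 | 15/16 + 40/80 = 1.44 | 0.52 |
| 160 | 15/16 + 40/160 = 1.19 | 0.25 |

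**Effect on the correlation (simulation, n = 30).** Assumptions: weight 55-120 kg; plasma volume 40 mL/kg; donor titre median 160 (SD 1.5 log2); day-0 titre median 40 (SD 2 log2); lowest dilution 1:20; no endogenous rise. The test is Spearman correlation of dose/kg with log2 change. Entries are the chance of p < 0.05, with endpoint or interpolated titres used for both plasma and recipient.

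| Assay noise (log2 SD) | Twofold: endpoint / interpolated | Fourfold: endpoint / interpolated |
|---|---|---|
| 0.15 | 81% / 91% | 57% / 91% |
| 0.3 | 68% / 74% | 50% / 71% |
| 0.5 | 44% / 50% | 30% / 49% |

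Repeat runs differ by a few points, which gives gains of about 5-11 points for twofold and 20-35 for fourfold steps. Interpolation was never worse.

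- *Ties.* With twofold steps, no change is recorded in about 57-70% of patients at noise 0-0.3 and about 47% at noise 0.5. About 15-16% remain tied after interpolation because both samples are below 1:20.
- *Dependence on the donor titre.* With different assumptions (Vp 3.0 L, no assay error, from no to all recipients seropositive), the tied share runs from 86-91% at a donor median of 80 to 25-45% at 640.
- *Source of the loss.* With twofold steps and noise 0.15, interpolating only recipient titres gave 89% power; interpolating only donor titres gave 82%. Most of the loss therefore comes from the recipient read-out.
- *Endogenous rise.* Adding an assumed day-1 rise from the patient's own response cuts the twofold gain to about 2-5 points. If that rise is half-normal with scale 1 log2, the fourfold gain is still 14-26 points; with scale 0.5, the twofold gain is 3-11 points.

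**The case against.** The strongest reply is that the plan never says recipient titres are endpoints. The word qualifies only the plasma titre, and using the same assay does not fix the same read-out. Interpolated recipient titres would be consistent with section 8, and there would then be little loss. This stands. It makes the point conditional, but it also shows the gap: nothing in the plan rules out a stepped read-out for both.

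Second, the benefit can be small. With twofold steps it is modest, an endogenous rise shrinks it further, and the large gains need a fourfold series that no section mentions. This also stands. Section 13.2 moreover makes change at days 1, 3, 7 and 14 the primary statistical endpoint, with repeated-measures and mixed models, so the day-1 correlation is not the only analysis. The plan also concedes limited power.

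A reader might go further than the documents allow in three ways:

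- *That a unit adds 1/16 of the donor titre.* No plasma volume is given (13.1.1 mentions only "NAb dosing calculated in units/BSA and units/calculated plasma volume"), and 1/16 of the donor titre holds only at 3 L and a zero baseline.
- *That every rise below twofold is lost.* It is recorded with probability log2(fold).
- *That the four unchanged patients in the cited study demonstrate the mechanism.* Section 2 gives no baselines, dilution step or sampling time for them. They are consistent with it and prove nothing.

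**Conclusion.** The point holds in conditional form. The primary dose is defined on an endpoint titre, and the recipient read-out is left open. If recipient titres are read in steps, a twofold day-1 rise needs a donor titre about 12-25 times the recipient's for plasma volumes of 2.0-4.5 L, and smaller rises are only partly recorded. The cost to the correlation ranges from slight (twofold steps with an endogenous rise) to substantial (fourfold steps).

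The power figures rest on assumed titre distributions, noise and dilution series and are illustrative. Mixing also ignores loss of antibody outside the plasma, which would make the rise smaller. The documents do not support saying that the study will miss the relationship or that the dose definition alone causes the loss. The change is still worth making, because the better read-out should come from counts already planned.

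**What to change.** 1. In 1.1.2 and 13.1.1, replace the endpoint titre with the interpolated 50% neutralization titre, from a curve fitted to the plaque counts across dilutions.
2. Add to 7.1.1 and section 8, which do not now state a read-out, that the same interpolated titre is used for every recipient sample and is analysed on the log scale.
3. State the starting dilution, the dilution factor, the handling of values below the lowest dilution, and what counts as a change.
4. List endpoint titres as a secondary descriptor, for comparison with published series.

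The cost is a wording change and a little more analysis. No new sample or assay should be needed, provided enough dilutions give countable wells; the laboratory should confirm this. Interpolated values are less directly comparable with published endpoint titres, which is why both should be listed. The change does not help pairs in which both samples lie below the lowest dilution.

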1.2. Secondary, exploratory objectives

- 1.2.1. To evaluate the safety of convalescent plasma (CP) administration in hospitalized COVID-19 patients
- 1.2.2. To evaluate viral shedding of SARSCoV-2 in nasopharyngeal or nasal samples before and on days 3, 7, and 14 after CP transfusion
- 1.2.3. To perform genomic analysis of the SARS-CoV-2 from patients before and after treatment with CP transfusion
- 1.2.4. Determine cumulative incidence of disease severity (transfer to ICU, type of respiratory support, LOS, and mortality)

2. Background

Passive antibody treatment involves the administration of antibodies against a specific infection to a susceptible individual to treat or ameliorate the severity of the disease caused by the infectious agent. Plasma from patients that have recovered from the infection is harvested and administered to the non-immune. The use of this modality of treatment dates back to the 1890's, but its popularity decreased during the antibiotic era.(Casadevall, 2020)

During the current SARSCoV-2 pandemic, with its associated high mortality and morbidity and the lack of demonstrated and effective treatment or vaccine, the induction of immunity with the transfusion of convalescent plasma offers a therapeutic alternative.

Convalescent plasma was studied during the SARS epidemic in 80 patients in Hong Kong.(Cheng 2005) Those treated before day 14 had improved prognosis defined by discharge from hospital before day 22, consistent with the notion that earlier administration is more likely to be effective. There is also anecdotal information on the use of convalescent serum in seriously ill individuals. Three patients with SARS in Taiwan were treated with 500 mL convalescent serum, resulting in a reduction in serum virus titer, and each survived (Yeh 2005)

PROTOCOL TITLE: Open, non-comparative pilot study to provide access to treatment with investigational convalescent plasma and measure antibody levels in patients hospitalized with COVID-19

There are reports that convalescent serum was used for therapy of patients with COVID-19 in China during the current outbreak. In an open label study, 5 patients received transfusion with convalescent plasma with a SARS-CoV-2– specific antibody (IgG) binding titer greater than 1:1000 (end point dilution titer, by enzyme-linked immunosorbent assay [ELISA]) and a neutralization titer greater than 40 (end point dilution titer) that had been obtained from 5 patients who recovered from COVID-19 (Shen 2020). Convalescent plasma was administered between 10 and 22 days after admission. In this preliminary uncontrolled case series of 5 critically ill patients with COVID-19 and ARDS, administration of convalescent plasma containing neutralizing antibody was followed by improvement in their clinical status.

In another study, 10 patients were treated with one dose of 200 mL convalescent plasma (CP) derived from recently recovered donors with the neutralizing antibody titers above 1:640 in addition to maximal supportive care and antiviral agents Duan 2020). The clinical symptoms were significantly improved along with increase of oxyhemoglobin saturation within 3 days. Several parameters tended to improve as compared to pre-transfusion, including increased lymphocyte counts ($0.65 \times 10^9/L$ vs. $0.76 \times 10^9/L$) and decreased C-reactive protein (55.98 mg/L vs. 18.13 mg/L). Radiological examinations showed varying degrees of absorption of lung lesions within 7 days. In none of these two trials serious adverse events associated with the use of CP were reported.

More recently, the FDA has endorsed the use of CP under an emergency IND, specific guidance on donor and potential recipient selection has been published. (<https://www.fda.gov/media/98616/download>)

Little is known about how the treatment with CP affects the recipient's immune response to the infection with SARS-CoV-2. What levels of neutralizing antibodies (NAb) are obtained in patients transfused? Is there association between neutralizing antibody titers and clinical outcomes? In the study by Duan et al, with 10 patients treated with CP, the neutralizing antibody titers of five patients increased and four patients remained at the same level after CP transfusion. However, neither study performed a comparison between the NAb dosing adjusted for body weight versus resulting NAb levels in recipients.

In light of limited availability of CP and the urgent need for promising therapies for COVID-19, it will not be initially feasible to measure NAb titers in the convalescent plasma (CP) prior to plasma administration or to adjust the volume of CP to be administered based on NAb titer in the CP or the body weight or plasma volume of the recipient. However, while this study does not involve administration of plasma with known NAb titer, information gained from the current study may help inform dosing in the future, including in potential dosing modifications that could be submitted via a protocol modification.

PROTOCOL TITLE: Open, non-comparative pilot study to provide access to treatment with investigational convalescent plasma and measure antibody levels in patients hospitalized with COVID-19

The correlation between the levels or titers of neutralizing antibodies after CP transfusion and viral shedding has not been sufficiently explored. Are certain levels of neutralizing antibodies associated with viral clearance? In the study by Duan et al., the viral load was undetectable after transfusion in seven patients who had previous viremia (Duan et al.) We propose to monitor viral shedding in respiratory secretions after CP transfusion. The presence of the virus is relevant for transmission, especially in the hospital setting.

3. Study Design

This is an open label pilot study designed to provide access to treatment with investigational convalescent plasma and assess the relationship between NAb titers in the investigational convalescent plasma compared to changes in NAb levels in the recipient in hospitalized patients with COVID-19.

4. Inclusion and Exclusion Criteria

Inclusion Criteria for Enrollment

1. Patients must be 18 years of age or older.
2. Hospitalized with COVID-19 respiratory symptoms and confirmation via COVID-19 SARS-CoV-2 RT-PCR testing. If COVID-19 test results are pending or done at enrolment, test results must be positive prior to administration of convalescent plasma.
3. Patient (or legally authorized representative, LAR) is willing and able to provide written informed consent and comply with all protocol requirements.
4. For patients unable to consent, consent by the legally authorized representative (LAR) may be obtained by phone.

Exclusion Criteria

1. Female subjects with positive pregnancy test or breastfeeding.
2. Receipt of pooled immunoglobulin in past 30 days.
3. Contraindication to transfusion or history of prior severe allergic reactions to transfused blood products
4. On ECMO or in refractory shock at entry

5. Number of Subjects

This pilot aims to explore safety and measure antibody levels in patients treated with CP. We aim to enroll 30 subjects to ensure the estimate of *neutralizing antibodies* to be within 20% margin of error.

PROTOCOL TITLE: Open, non-comparative pilot study to provide access to treatment with investigational convalescent plasma and measure antibody levels in patients hospitalized with COVID-19

6. Study Timelines

Hospitalized patients will be enrolled as soon as their COVID-19 diagnosis is confirmed, using approved diagnostic methods, and will be followed until hospital discharge or death. Patient enrollment will start immediately after IRB approval. We anticipate a 3-month enrollment. The study will continue for another 24-months after the last enrollment during which we will be able to process and analyze data, and disseminate findings.

7. Study Endpoints

7.1. Primary endpoint:

- 7.1.1. Titers of SARS-CoV-2 neutralizing antibodies measured by focus reduction neutralization test (FRNT) at days 0 (pre-transfusion), 1, 3, 7 and 14 days of CP transfusion.

- 7.1.2. Availability of convalescent plasma

7.2. Secondary endpoints:

Clinical outcomes:

- 7.2.1 Serious adverse events
- 7.2.2 SARCoV-2 viral shedding in nasopharyngeal samples determined by RT-PCR
- 7.2.3 Genomic variations of SARS-CoV-2 before and after CP transfusion
- 7.2.4 Transfer to ICU
- 7.2.5 Type and duration of respiratory support (and other ICU support including ECMO, CRRT) in ICU
- 7.2.6 Cardio-circulatory arrest (at any time)
- 7.2.7 ICU mortality and LOS
- 7.2.8 Hospital mortality and LOS
- 7.2.9 Ventilator-free days
- 7.2.10 In hospital mortality
- 7.2.11 Titer of other functions of antibodies, including antibody-dependent cell-mediated and complement-dependent cytotoxicity

7.3. Safety Endpoints:

- 7.3.1 Rapid deterioration of respiratory or clinical status on transfusion of SARS-CoV-2 convalescent plasma.
- 7.3.2 Cumulative incidence of serious adverse events during the study period: febrile non-hemolytic transfusion reaction, allergic transfusion reaction, transfusion related acute lung injury (TRALI), transfusion associated circulatory overload (TACO),

PROTOCOL TITLE: Open, non-comparative pilot study to provide access to treatment with investigational convalescent plasma and measure antibody levels in patients hospitalized with COVID-19

transfusion related infection, hemolytic transfusion reaction or evidence of antibody dependent enhancement of infection (ADE).

8. Research Setting

The study will be conducted in the University of New Mexico Hospital. Patients admitted to the COVID-19 units including the emergency department, regular wards and intensive care units will be enrolled. Patients will be identified from the TriCore Laboratory testing result portal available to the research team or upon notification by providers in the participating institutions. Approval by the treating provider will be requested before patient enrollment and consent.

There is no external sponsor for this research. Immune assays and genomic studies will be performed utilizing existing resources within the [name] and [name] laboratories in the Center for Global Health.

SARS-CoV-2 neutralizing antibody titers will be measured using the focus reduction neutralization test (FRNT) in [name] Laboratory, Center for Global Health (CGH), UNMHSC. Neutralization assays will be conducted using methods already established in the [name] laboratory. Briefly, serial dilutions of plasma will be incubated with 50-100 pfu of SARS-CoV-2 at equal volumes for 1 hour and added to Vero E6 cells, followed by overlaying with agarose. Two days later cells will be fixed with 4% formaldehyde, stained with crystal violet, and plaques will be counted. Other functions of antibody, including antibody-dependent cell-mediated cytotoxicity and complement-dependent cytotoxicity, will be ascertained using established methods.

Virus sequencing will be performed in the laboratory of [name] in the Center for Global Health using the PCR-based NGS sequencing protocol described by the ARTIC Network <https://artic.network/ncov-2019>

9. Resources Available

9.1. Principal investigator and co-investigators are experienced Pulmonary, Critical Care, Infectious Disease ID Pharmacists, Virologist or Transfusion Medicine specialists with ample experience in conducting clinical trial and with the use of CP in previous clinical studies (GM):

- 9.1.1. [name], is a Pulmonary and Critical Care Medicine specialist and is the Chief of the Division of Pulmonary at UNMH
- 9.1.2. [name], is an Infectious Disease Attending and is the Chief of Infectious Diseases at UNMH.

